4.6 Blind Review

Important deviations from the protocol and validity findings and the resulting assignment of subjects to the analysis sets (see Section 5.1) are agreed upon in the blind review meeting (BRM). The documentation of important deviations, validity findings and the assignment of subject data to analysis sets will be performed according to the sponsor's applicable Standard Operating Procedures and/or Instruction Manuals. The definition for important deviations and validity findings will be provided in the 'Specification of assessment criteria and identification requirements' before unblinding the data.

Identification of important deviations and validity findings will be done periodically while the study is running, concluding with the completion of the final list during the BRM. Any changes to the statistical analysis prompted by the results of BRM will be documented in an amendment and, if applicable, in a supplement to this SAP.

The list of important deviations and validity findings will only be final after assessment of conditional findings, which are validity findings that can only be identified after unblinding of study treatment.

5. Analysis Sets

5.1 Assignment of analysis sets

Final decisions regarding the assignment of subjects to analysis sets will be made during the blind review of study data and documented in the final list of important deviations, validity findings and assignment to analysis set(s) (see Section 4.6).

The following statistical analysis sets will be defined:

Full analysis set (FAS): All randomized subjects, excluding randomized subjects who did not start TP1 due to the study being temporarily paused. Subjects will be analyzed as randomized.

Per protocol set (PPS): All subjects in the FAS without any validity findings impacting the primary efficacy variable in TP1.

Safety analysis set (SAF): All subjects who took at least 1 dose of study drug based on 'Study Drug Exposure' eCRF page. Subjects will be analyzed as treated. Mistakes in the administration of study drug may affect the assignment to treatment. In general, subjects who receive a different study drug to the one they were randomized to will be assigned to the treatment most often received.

The primary efficacy variable will be analyzed on the FAS and PPS, whereby the analysis on the FAS is considered to be the primary one. Safety analyses, medical history and concomitant medication will be performed on the SAF. Demographic data, baseline characteristics, exposure and compliance will be analyzed on the FAS, SAF and PPS. The FAS will be used for the display of all other variables. Analyses on the PPS will be additionally conducted as sensitivity analyses for selected secondary efficacy variables.

All screened patients who are not included in the FAS, will be used solely in disposition tables, and will be listed only in Section 16 of the clinical study report, as described elsewhere.

6. Statistical Methodology

6.1 **Population characteristics**

In general, descriptive statistics will be presented for variables defined in this section. For continuous variables, number of observations, mean, standard deviation, minimum, median, and maximum will be presented. For categorical variables, number and percentage of subjects will be presented. Listings will be provided as appropriate.

6.1.1 Subject validity and disposition

The following data related to subject validity and disposition will be summarized overall and/or by treatment group, if applicable and not specified otherwise:

- Screening failures
- Number of subjects enrolled overall, by country and by study site
- Number and percentage of subjects randomized,

- who received at least one dose of study drug (based on 'Study Drug Exposure' eCRF page),
- for whom study drug was never administered (based on 'Study Drug Exposure' eCRF page),
- who completed and did not complete the study, whereby completed refers to the completion of all phases of the study including the 'last visit' or 'the last scheduled procedure shown in the Schedule of Activities'.
- Number and percentage of subjects who completed and discontinued each epoch with the reasons for discontinuation
- Number and percentage of subjects who discontinued study drug with the reasons for discontinuation
- Subject validity and primary reasons for exclusion from analysis set
- Number and percentage of subjects who performed adrenal monitoring, skin monitoring and endometrial monitoring within the safety closeout visit, and further details about the participation in the safety closeout visit.

A listing of the subjects' assignment to the FAS, SAF and PPS and the reasons for exclusion will also be provided by treatment group.

6.1.2 Demographics and baseline characteristics

All demographic and baseline characteristics will be summarized by treatment group (including pooled treatment group A1+B2). The descriptive statistics will be presented for the FAS, SAF and PPS.

Demographic and baseline assessments to be summarized will include:

- Age (at inclusion), region/country, race, ethnicity
- Weight (kg), height (cm), body mass index (BMI; kg/m²)
- Categorized BMI (< 18.5, 18.5 to < 25, 25 to < 30, ≥ 30 kg/m²)
- Smoking and alcohol consumption
- Educational level (i.e., level of education, years of school and professional education)
- Baseline MBL (by AH method/MP) and categorized MBL group (≤150 mL, >150 to 300 mL, > 300 to 500 mL and > 500 mL)
- Volume of 3 largest fibroids and location of largest fibroid (International Federation of Gynecology and Obstetrics [FIGO] classification) by ultrasound (mL)
- Largest diameter of fibroid by ultrasound (mm)
- Uterine volume by ultrasound (mL)
- Endometrial thickness by ultrasound (mm)
- Hemoglobin (g/dL)

Demographic and baseline characteristics will be summarized also for the following subgroups:

- By region/country (Japan, US, other countries)
- By ethnicity
- By race

6.1.3 Medical history

For medical history the Medical Dictionary for Regulatory Activities (MedDRA; current version at the time of analysis) will be used. Medical history findings (i.e., previous diagnoses, diseases or surgeries) not pertaining to the study indication, starting before signing of the informed consent and considered relevant to the study will be tabulated by primary system organ class (SOC) and preferred term (PT) by treatment group. Medical history will be presented for SAF.

All new or worsened findings after signing the informed consent should be documented on the AE eCRF page.

6.1.4 Reproductive, menstrual, and fibroid history

Reproductive and menstrual history will include information on age at menarche (in years), number of pregnancies, number of births, years since last birth or abortion and inability to conceive (at any time and during the last 1 year) and duration of unsuccessful attempts (in months).

Fibroids history will include information on family history, time since initial diagnosis (in months), and reason for initial diagnosis, current and past symptoms, and previous medical treatments and procedures relevant for uterine fibroids, if applicable.

In addition, any performed procedures for uterine fibroids or symptoms of uterine fibroids and the consideration of surgical procedures within the next 12 months in case of remaining symptoms (as they are at screening) will be summarized.

These variables will be analyzed descriptively, separately for each treatment group based on the SAF.

6.1.5 Heavy menstrual bleeding questions

This set of questions has been developed as a tool to identify women with HMB. It will be used at Visit 1 and the responses can be entered directly into electronic data capturing system RAVE, which will be considered as primary source data. The questionnaire includes 14 questions in total. The response (yes/no) to each question will be presented descriptively in frequency tables separately for each treatment group based on the SAF.

6.1.6 Exposure and compliance to study drug

Exposure, treatment duration and compliance to study drug will be analyzed descriptively based on the SAF, FAS and PPS. They will be presented by treatment period and overall, (i) by treatment group and (ii) by study drug. Overall treatment duration will be shown including and excluding treatment break. Both study drug exposure and compliance will be calculated

separately based on the eDiary data as well as on the eCRF (namely the 'Study Drug Exposure' and the 'Drug Accountability' pages).

Subject's *exposure* to the study drug will be calculated as total number of tablets taken during a time frame (i.e. either a specific treatment period or both treatment periods combined), using information from the 'Drug Accountability' eCRF page and the subject's eDiary. Missing numbers of tablets taken based on eCRF page will not be replaced, while missing numbers of tablets taken based on eDiary will be replaced with 0.

The *treatment duration* is defined as the number of days from the day of first study drug intake up to and including the day of last study drug intake in the treatment period of interest. Treatment duration will be calculated separately for the two treatment periods. In addition, it will be computed for both treatment periods combined excluding the time for treatment break and for the treatment phase (i.e. including the break). For the latter, treatment duration per specific study drug is calculated from start of TP1 until start of TP2 and from start of TP2 until end of TP2 (i.e. the break is included in the duration of TP1). If a patient discontinued before TP2, treatment duration is calculated from start to end of TP1.

The days of first and last study drug intake will be taken from the 'Study Drug Exposure' eCRF page. Missing dates in the eCRF will not be replaced.

Treatment compliance of a subject is defined as the total number of tablets taken during a specific time frame (i.e. the exposure) divided by the treatment duration (in days) for that time frame, and will be given in percent. Compliance calculation is derived from exposure based on (i) the eCRF and (ii) eDiary and treatment duration (excluding breaks) based on the eCRF, as described above.

Compliance will be derived as follows:

 $Compliance = \frac{Number of tablets taken}{Treatment duration} \times 100\%$

6.1.7 Prior, concomitant and post-treatment medication

For prior, concomitant and post-treatment medications, the following definitions in accordance with the Global Standards Catalogue V4.0 will be used in the analysis (see Figure 6–1):

- *Prior medication*: Medication taken before start of the study drug intake, i.e. before start of TP1 (regardless of when it ended).
- *Concomitant medication*: Medication taken during treatment phase, i.e. between first and last study drug intake (regardless of when it ended).
- *Post-treatment medication*: Start of medication is after the treatment phase, i.e. after last study drug intake.

In case it's not clear if a medication is prior, concomitant or post-treatment (for example, due to partially missing dates), medication will be classified as "concomitant".

[figure not shown]

Figure 6–1: Categories of medication (example)

Categories are prior medication (A, B, C), concomitant medication (B, C, D, E) and post-treatment medication (F). Source: Global Standards Catalogue V4.0

Medication, recorded as prior, concomitant or post-treatment medication in the eCRF, will be coded according to the World Health Organization Drug Dictionary WHODRUG GLOBAL B3 (initially September 1, 2017, within Bayer referred to as '2017SEP'), to the respective Drug Codes with their corresponding Anatomical Therapeutic Chemical (ATC) classification.

The number of subjects taking prior, concomitant or post-treatment medication will be analyzed using frequency tables. Analysis of prior, concomitant and post-treatment medication will be done on the SAF. Prior, concomitant and post-treatment medication will be shown by treatment group.

6.2 Efficacy

The following sections describe the efficacy analyses of primary, secondary, and other efficacy variables in detail. Further variables that were captured during the study will be either analyzed descriptively or displayed in subject listings.

The primary efficacy variable and secondary efficacy variables will be calculated based on the AH method. Other efficacy variables related to MBL will be calculated based on both the AH method and MP. If an endometrial biopsy was conducted during a time period for which bleeding will be assessed, bleeding or 'spotting' on the day of biopsy and the 3 days thereafter will not be considered in the derivation of any variables that belong to primary, secondary or other efficacy variables. Thus, prior to the assessment of bleeding variables, such as amenorrhea, for example, the AH and UF-DBD entries during those days will be set to 0 mL and "No vaginal bleeding", respectively.

For the confirmatory efficacy analysis, a hierarchical testing approach will be applied, involving the primary efficacy variable amenorrhea (yes/no) and the first three secondary efficacy variables HMB response, time to onset of amenorrhea, and time to onset of controlled bleeding. These tests always include a comparison of vilaprisan 2 mg versus placebo:

After 12 weeks of treatment in TP1:

Comparison of vilaprisan 2 mg in pooled treatment groups A1 and B2 (as the treatments are the same and pooling increases the power) vs. placebo in treatment group B1.

In total, four tests will be carried out each to an alpha level of 0.05, see also Figure 6–2: First, the test for the primary efficacy variable amenorrhea (yes/no) will be carried, followed by the test for HMB response (yes/no), the test for time to onset of amenorrhea, and finally, the test for onset of controlled bleeding. As the hierarchical testing procedure follows a fixed sequence, it stops as soon as any of these tests cannot be rejected to an alpha level of 0.05, and all further tests after failing to reject one null hypothesis in the testing sequence will be considered exploratory. This fixed sequence procedure accounts for the multiplicity created by carrying out multiple tests.

[figure not shown]

Figure 6–2: Hierarchical testing strategy for the confirmatory efficacy analysis

Abbreviations: HMB: Heavy menstrual bleeding, CMH: Cochran-Mantel-Haenszel, H: Hypothesis to be tested related to the amenorrhea (H₁), HMB response (H₂), time to onset of amenorrhea (H₃) or time to onset of controlled bleeding (H₄), TP: Treatment period, A1: Vilaprisan 2mg; 2 treatment periods of 12 weeks, B1: Placebo; 1 treatment period of 12 weeks and Vilaprisan 2mg; 1 treatment period, B2: Vilaprisan 2mg; 1 treatment period of 12 weeks and placebo; 1 treatment period.

The study will be considered successful if at least superiority of vilaprisan 2 mg vs. placebo in Treatment Period 1 (TP1) based on the primary efficacy variable can be demonstrated. In general, superiority of vilaprisan treatment is shown if the respective null hypothesis is rejected to a local alpha level of 0.05 and point estimates of treatment effect favor vilaprisan.

The primary analysis will be conducted based on the FAS (see Section 5.1).

6.2.1 **Primary efficacy variable**

The primary efficacy variable is amenorrhea (yes/no), defined as MBL <2 mL during the last 28 days of treatment. Evaluation of MBL will be based on AH method for a treatment period of interest.

The primary efficacy variable will be derived after the imputation of missing values described in Section 4.3.

If after the imputations described in Section 4.3 and considering potential biopsies, neither of the AH values for the last 28 days are missing, AH values and bleeding intensities of the last 28 days of a treatment period are used to derive the primary efficacy variable.

If, in contrast, there are AH values in the last 28 days of treatment which are still missing (i.e., where an imputation was not possible), it is further studied whether the corresponding bleeding intensities of the UF-DBD are missing on the same day(s) as well.

- (a) If the bleeding intensity is not missing and only the AH value is missing, the bleeding intensity must be at least 'mild', because for 'no vaginal bleeding' and 'spotting' the AH value would have been imputed with 0 mL. Accordingly, it must be assumed that bleeding has occurred on these day(s). Therefore, the subject is considered as not having amenorrhea. Step b) will then not be applied irrespective of whether there are also days for which both, the bleeding intensity and the AH value, are missing.
- (b) If both, the bleeding intensity and the AH value, are missing for any of the last 28 days, the 28-day period will be extended: The left margin of the 28-day period will be displaced backwards in time and step-wise until the required number of 28 non-missing AH values are included. The left margin may be displaced backwards at maximum up to the end of the first bleeding episode when treatment was started in respective treatment period.

Considering this time window, a subject will be considered as not having amenorrhea if

- i) the sum of the non-missing (i.e. original or imputed) AH values is ≥ 2 mL, or
- ii) there is at least one day with missing AH value and bleeding intensity of 'mild' up to 'very severe' after having applied the imputation rules, or
- iii) the subject did not complete at least 8 weeks of treatment.

If neither of i), ii) or iii) applies, the subject will be considered as having amenorrhea.

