### **10.3.3 Missing data/drop outs**

*This section was changed in Amendment 1, see Section 15.1.1*

For the primary efficacy variable and secondary efficacy variables included in the testing strategy described in Section 10.3.2.2, it is assumed that data measured with the AH method will be only available on days when vaginal bleeding occurred. To differentiate missing AH data and days without vaginal bleeding the bleeding intensity collected in the UF-DBD will be used.

Missing bleeding data in the subject diaries will be imputed. For the UF-DBD, the worst case approach will be used for missing bleeding intensity for the single or two consecutive missing days (i.e., the maximum of the bleeding intensities of the day before and the day after the missing day[s] will be assumed).

If an endometrial biopsy was conducted during the time period under treatment, bleeding on the day of biopsy and the 3 days thereafter will not be considered as day(s) with bleeding/spotting and the AH value will be set to 0 mL. For the primary efficacy variable amenorrhea and the secondary efficacy variable HMB response, subjects will be defined as not having amenorrhea/not being a HMB responder if they did not complete at least 8 weeks

of treatment. Generally, in case a daily bleeding intensity is recorded with the UF-DBD as “no vaginal bleeding” or “spotting”, the missing AH value for this day will be set to 0 mL.

For days with bleeding intensity of “mild” or higher in the UF-DBD, missing AH values will be replaced by the mean value of AH values of the days with the same bleeding intensity. In case there are no AH values with the same bleeding intensity, the mean of the AH values of next higher intensity will be used. In case there is no intensity higher than the bleeding intensity of the missing AH values available, either, no replacement for the missing AH values will be done for such days; but if at least one such day occurs within the respective 28 days of treatment for a subject, the subject will be considered as not having amenorrhea/not being a HMB responder.

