Furthermore, the last days under treatment with at least 28 days with non-missing bleeding intensity/AH values under treatment until the initial bleeding episode when the treatment started (after the imputations above) (without missing information: Days 57 to 84 under treatment) will be used to calculate the primary efficacy variable and the secondary efficacy variable HMB response. After these imputations a subject will be considered as not having amenorrhea in the presence of missing AH values if the sum of all non-missing AH values is not lower than 2 mL or if for missing AH values the bleeding intensity in the UF-DBD is “mild” or higher, otherwise the subject will be considered as having amenorrhea. An equivalent approach as described for the amenorrhea rate will be applied for the secondary variable HMB response, ie, after the imputations as described above a subject will be considered as not being a HMB responder in the presence of missing AH values if the sum of all non-missing AH values is  $\geq 80$  ml or the reduction of blood loss is  $\leq 50\%$  as compared to baseline or if for missing AH values the bleeding intensity in the UF-DBD is “mild” or higher, otherwise the subject will be considered as a HMB responder.

For the secondary variables onset of amenorrhea and onset of controlled bleeding the first 28 days with non-missing bleeding/AH values until the last 28 days with non-missing bleeding/AH values under treatment will be considered. An analogous approach as described above for the primary efficacy variable and the secondary efficacy variable HMB response will be applied to assess the bleeding status for each of these 28-day windows in terms of amenorrhea and controlled bleeding. If a subject does not achieve amenorrhea or controlled bleeding until end of treatment the subject will be considered as censored for the respective endpoint.

Sensitivity analyses will be conducted to evaluate the impact of missing data. These will be described in the SAP.

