6.2.1.2.2 Analysis based on alternative missing data imputation strategy

The impact of missing data will be investigated in the FAS (according to the intention to treat principle) with multiple imputation, using a pattern-mixture framework as described by the National Research Council (NRC 2012) [7]. In the primary analysis, it is assumed that values in the UF-DBD or for the AH method are missing at random (MAR), i.e., they only depend on observed outcomes and can thus be imputed based on the observed data. However, it is possible that missing values are systematically different from observed values because patients are dissatisfied with their treatment and are consequently more likely to withdraw from the study, for example. If the differences between missing and observed values do not balance out between the treatment groups, then this creates a bias in the treatment effect. Therefore, this sensitivity analysis serves to examine the missing data mechanism and explore different scenarios under a MNAR (Missing Not at Random) assumption where an outcome depends on the fact whether it is observed or not and missing outcomes can thus differ systematically from observed outcomes by treatment group.

For the purpose of this sensitivity analysis for missing data, the standard procedure of imputing intermittent single or two consecutive days with missing UF-DBD bleeding intensities and the replacement of missing daily AH values with 0 mL for bleeding intensities of not more than 'spotting' are kept as sensible approaches because nothing out of line is expected to happen in the time frame of one or two days. In contrast to the primary analysis, however, days with biopsies and the three days thereafter will not be considered with an AH value of 0 mL (assuming no bleeding), but will be considered missing since the AH values on those days if the patient had not had the biopsy are unknown. This rule and further rules used to impute missing data in the primary analysis will be challenged with this analysis using multiple imputation in a pattern-mixture approach.

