Subjects are sorted into three categories based on the available UF-DBD and AH information from Day 57 to 84 of the TP1 (or the last 28 days of TP1, if study drug was taken for more than 84 days). Those three categories are comprised of clear responders and clear non-responders (after the initial minimal imputation rules described above) as well as subjects with unclear response status. A clear responder for amenorrhea is defined as a subject

- who has only UF-DBD bleeding intensities of no more than 'spotting' AND
- for whom the sum of daily AH values is less than 2 mL AND
- for whom there are no missing values for either the AH method (daily values) or the UF-DBD bleeding intensities.

As opposed to this definition, a clear non-responder for amenorrhea is defined as a subject

- who has at least one bleeding intensity of 'mild' or higher OR
- for whom the sum of daily AH values is equal to or higher than 2 mL.

All response criteria are set in relation to the planned time frame for the assessment of the primary efficacy variable, i.e., Day 57 to Day 84 of the TP1. An exception is made when a subject's TP1 is longer than 84 days. In this case the last 28 days of TP1 are used for the assessment.

A subject is considered as unclear responder for amenorrhea (and thus having a missing outcome) if in the relevant time frame, all the subject's bleeding intensities do not exceed 'spotting' and the sum of daily bleeding intensities is below 2 mL, but there are still missing values among both the UF-DBD bleeding intensities and the daily AH values between Day 57 and 84 of the TP1. Therefore, it is still possible that replacement of the missing bleeding information turns an apparent responder into a non-responder for amenorrhea, signifying that no clear assessment about the response status can be made.

A descriptive analysis of the number of subjects in each response category will be supplied by treatment group.

Missing data imputation will only be applied to subjects with unclear response status, whereas not the AH values will be imputed but the response status. Response status of subjects with unclear outcome are generated in a three-step process [8] by

- 1) Estimation of individual log-odds of amenorrhea for all patients from a logistic regression model, which is an imputation model fitted based on data of clear responders and non-responders,

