6.2.2 Secondary efficacy variables

The secondary efficacy variables are defined in the following. The confirmatory analysis of selected secondary efficacy variables will be performed only for data from TP1. In addition, secondary efficacy variables will be analyzed descriptively for both treatment periods.

• Heavy menstrual bleeding (HMB) response: HMB response is defined as MBL <80.00 mL during last 28 days of treatment and >50% reduction from baseline (assessed by AH method). Missing AH data will be imputed as explained in Section 4.3.

If an endometrial biopsy was conducted, bleeding on the day of intervention and the 3 days thereafter will not be considered in this evaluation, i.e., bleeding/'spotting' on the day of biopsy and 3 days thereafter will not be considered as day(s) with bleeding/'spotting' and AH values will be set to 0 mL.

After imputing missing bleeding intensities and AH values (see Section 4.3) and considering potential biopsies, the 28-day period will be extended in case there are still any AH values missing in the last 28 days (similar to the description in Section 6.2.1 b); a) will not be applied). Based on the 28-day period a subject will be considered as not being an HMB responder if

- i) the sum of the non-missing (i.e., original or imputed) AH values is \geq 80.00 mL *or* the reduction of blood loss is \leq 50% as compared to baseline or
- ii) the subject did not complete at least 8 weeks of treatment.

If neither of i) or iii) applies, the subject will be considered as an HMB responder.

• Time to onset of amenorrhea: Onset of amenorrhea is defined by the first day for which the MBL for all subsequent 28-day periods up to the end of a treatment period is <2 mL (amenorrhea defined similar to primary endpoint). The first 28 days with non-missing AH values until the last 28 days with non-missing AH values under treatment will be considered for deriving the time to onset of amenorrhea. An analogous approach as described for amenorrhea in the last 28 days of treatment (Section 6.2.1) will be applied to assess the amenorrhea status for each of the subsequent, overlapping 28-day periods within a treatment period (except for criterion iii), which does not apply). The censoring mechanism is assumed to be non-

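### For HMB response the SAP drops the protocol's non-responder rule for unmeasured bleeding days; a lesser gap is that fewer than 28 usable days has no stated outcome

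*SAP*

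**What the plan says.** **HMB response.** Protocol 10.3.3 replaces a missing AH value on a day of mild or heavier bleeding by the mean AH value of days with the same intensity, or failing that the next higher intensity. If neither exists, no value is imputed, and one such day in the 28 days settles the outcome: "the subject will be considered as not having amenorrhea/not being a HMB responder". The section then repeats the non-responder consequence for HMB response.

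SAP 4.3.1 keeps the imputation steps but states the consequence for amenorrhea only. SAP 6.2.2 extends the HMB window backwards whenever AH values are still missing, "similar to the description in Section 6.2.1 b); a) will not be applied". It lists two failure criteria: i) at least 80 mL or a reduction of 50% or less, and ii) less than 8 weeks of treatment. It then closes: "If neither of i) or iii) applies, the subject will be considered as an HMB responder". Time to onset of controlled bleeding applies the HMB approach to each overlapping 28-day period. SAP Section 7 records only added descriptive variables.

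**Amenorrhea.** SAP 6.2.1 step (b) extends the window to collect 28 non-missing AH values, with a limit: "The left margin may be displaced backwards at maximum up to the end of the first bleeding episode". The failure criteria are i) a recorded sum of 2 mL or more, ii) a day of mild or heavier bleeding with missing AH, and iii) less than 8 weeks of treatment. Otherwise "If neither of i), ii) or iii) applies, the subject will be considered as having amenorrhea". Protocol 10.3.3 has the same default: "otherwise the subject will be considered as having amenorrhea".

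**The concern.** For HMB response, a day known from the diary to be a bleeding day, but with no measured volume, is a failure in the protocol and is skipped in the SAP. A programmer following the SAP would look further back for a quieter day and sum only what was measured. Heavy bleeding whose sanitary products never reached the laboratory can then count as response. The rule feeds the second and fourth tests of the fixed sequence, and the change is not declared.

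The lesser matter concerns subjects with neither diary nor AH for most of Treatment Period 1. Step (b) has no outcome for them if 28 values cannot be found, and criteria i) to iii) may all be silent, so the closing sentence makes them successes. Yet early discontinuation and unmeasured bleeding are scored as amenorrhea failures, and the multiple-imputation analysis in SAP 6.2.1.2.2 treats such a subject's outcome as missing.

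**Working it through.** The plan gives no missingness rate and no figure of its own on this point. Inputs from the documents: 84-day treatment period (Protocol 7.1); 52 subjects planned per group, so 104 vs 52 after pooling A1 and B2, split 50/25/25% by region (Protocol 10.4); the continuity-corrected CMH statistic with critical value 3.841 (SAP 6.2.1.1). Everything else is marked as assumed.

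**1. Dropped HMB rule.** Assumed subject: baseline 100 mL; treated 84 days; menses on Days 60-64 with two mild days of 5 mL each and three very severe days with no AH value; 0 mL on other days in the window; no AH value at very severe intensity on any of her days. Very severe is the top diary category, so no higher intensity can be borrowed.

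| Step | SAP 6.2.2 | Protocol 10.3.3 |
|---|---|---|
| Three unmeasured days | skipped; left margin moves from Day 57 to 57 - 3 = Day 54 | one such day is enough |
| Recorded sum | 5 + 5 = 10 mL (< 80 mL) | not needed |
| Reduction | (100 - 10)/100 = 90% (> 50%) | not needed |
| HMB response | **yes** | **no** |

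At the planned sizes one such subject moves the placebo rate by 1/52 = 1.9 points, or the pooled vilaprisan rate by 1/104 = 1.0 point.

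**2. Fewer than 28 usable days: how much must be missing.** Minimum missing days = (treated days - last day of first bleed) - 27. With the first bleed ending on Day 5 (assumed): 84 - 5 - 27 = 52 of 79 days. If treated only 56 days: 56 - 5 - 27 = 24 of 51.

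**3. Constructed case.** Assumed: treatment starts on bleed day 4, 5-day menses at 20 mL/day (100 mL, unchanged throughout), 28-day cycle, 84 days treated, diary and AH both stop for good after Day s. The first bleed ends on Day 2 and the next menses starts on Day 26.

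| Window limit | Amenorrhea = yes | HMB response = yes |
|---|---|---|
| Day after the last bleed day (Day 3) | s = 4 to 25 (2 to 23 usable days) | s = 4 to 27 |
| Last bleed day included (Day 2, 20 mL) | no s | s = 4 to 26 |

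So the amenorrhea result depends on whether the last day of the first bleed is inside the window. The HMB result hardly does. Under the first limit, HMB response at s = 27 has 40 mL recorded (60% reduction, yes) and at s = 28 has 60 mL (40%, no).

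**4. Effect on rates and tests.** Let f be the share of an arm affected (assumed 0, 5 or 10%, set separately by arm). Rate under the default = p(1 - f) + f; under failure scoring = p(1 - f). With assumed true rates 0.80 vs 0.10 (difference 0.70):

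| f vilaprisan / placebo | Default: difference | Failure scoring: difference |
|---|---|---|
| 10% / 10% | 0.82 - 0.19 = 0.63 | 0.72 - 0.09 = 0.63 |
| 10% / 0 | 0.82 - 0.10 = 0.72 | 0.72 - 0.10 = 0.62 |
| 0 / 10% | 0.80 - 0.19 = 0.61 | 0.80 - 0.09 = 0.71 |

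CMH on expected counts, over all combinations of f and both scorings:

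| True rates | 104 vs 52 | 52 vs 26 (assumed half size) |
|---|---|---|
| Amenorrhea 0.80 vs 0.10 | 49.9 to 69.5 | 23.3 to 32.7 |
| Amenorrhea 0.50 vs 0.10 (planning difference 0.4) | lowest 12.4, p = 0.0004 | lowest 5.5, p = 0.019 |
| HMB response 0.90 vs 0.33 (limits in Protocol 10.4) | 32.4 to 56.0 | 14.9 to 26.1 |

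Every value exceeds 3.841.

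**The case against.** On HMB response, the defence is that the case is narrow. SAP 4.3.1 first borrows from the same, then the next higher, intensity. AH was collected from screening onwards, and entry required two AH-measured bleeds above 80 mL. SAP 4.3.1 does not say whether values are borrowed from the subject or from the whole study; if from the study, the case all but disappears. Switching off step a) looks deliberate, and the stray iii) is probably a numbering slip, since SAP 6.2.2 (controlled bleeding) and 6.2.3.1 call the 8-week rule criterion ii). This limits how often the fault bites. It does not reconcile the two documents or declare the change. A reader might infer that any unreturned sample produces a false responder. The text does not support that: imputation must fail first, and the remaining recorded loss must still meet both response criteria.

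On amenorrhea, several stronger readings are tempting. One is that the SAP departs from the protocol; it does not, because Protocol 10.3.3 has the same default. Another is that absent data always give success; recorded loss of 2 mL or more, or a recorded mild or heavier day without AH, still gives failure. A third is that the default contradicts the SAP's statement that "it is assumed that values in the UF-DBD or for the AH method are missing at random (MAR"). That sentence concerns daily diary and AH values, so the tension is mild. Finally, the eDiary was reviewed between and at visits (Protocol 7.7), so gaps of this length should be rare, and SAP 6.2.1.2.2 already imputes such subjects and runs a tipping-point analysis. All of this stands and makes the amenorrhea matter minor.

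**Conclusion.** The HMB point holds and should be settled before unblinding. The SAP omits a failure rule that the protocol states, cites a criterion that does not exist, carries the omission into the fourth confirmatory test and does not declare it. That it can turn unmeasured heavy bleeding into response assumes imputation from the subject's own values and no AH value at that or the next higher intensity. How many subjects are affected cannot be told from the documents.

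The missing outcome for fewer than 28 usable days is a minor gap shared by both documents. Cases should be few, and in the scenarios tried, with 0 to 10% of subjects affected, no test conclusion changes. What can move is the reported rates and difference. A reader might infer that the default favours vilaprisan, or that failure scoring removes a bias. Neither follows: the default favours whichever arm has more such gaps; with equal gaps both scorings give the same difference; and with gaps only on vilaprisan failure scoring is further from the assumed 0.70 (0.62 against 0.72). The argument for failure scoring is consistency with criteria ii) and iii), not lack of bias.

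**What to change.** Before unblinding:

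1. Restore in SAP 4.3.1 and 6.2.2 the protocol's rule that a day of mild or heavier bleeding with a non-imputable AH value makes the subject an HMB non-responder. Apply it to the 28-day periods used for onset of controlled bleeding. State whether imputation draws on the subject's own values or the study's.
2. Correct the closing reference to iii) so that it matches the list. Adding the restored rule as a new iii) would leave the other references to criterion ii) valid.
3. State in SAP 6.2.1 whether the last day of the first bleed lies inside the window. Score fewer than 28 non-missing (observed or imputed) AH values after maximal extension as not amenorrheic and as HMB non-response.
4. Report affected subjects by arm, and record in Section 7 the change under item 3 and any departure from Protocol 10.3.3 that is kept.
5. Keep the 6.2.1.2.2 multiple-imputation and tipping-point analysis as the check. Say whether it also applies to HMB response, for which SAP 6.2.2.2 names only the per-protocol set.

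The cost is a few sentences and a small programming change. Item 3 does alter a derivation shared with the protocol after SAP 4.4 says the confirmatory efficacy data have been collected, so it must be made blind and documented. Reported rates may fall slightly in both arms. The difference may move either way and may be understated if the gaps are mainly on vilaprisan.
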